### 10.2. Subject Enrollment

A subject is considered enrolled in the study when it is confirmed they meet all pre-operative inclusion and no exclusion criteria, the ICF is signed and they have been implanted with the device. A subject must be followed for the full 24 months if the procedure was begun or completed with the study device. No study procedures, or data collection will be performed until informed consent form has been completed.

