4.1. Primary Objective

The primary objective of this investigation is to confirm the efficacy of ProGrip™ Self-gripping Polyester Mesh to reduce the incidence of incisional hernia within 24 months post-operatively in subjects undergoing procedure with midline laparotomies.

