Informed consent	X ²								
Pregnancy Test	X								
Subject demographics	X								
Relevant prior medical/surgical history	X								
Surgical Data									
Date of surgery		X							
Procedure indication		X							
Surgical technique for laparotomy closure		X							
Mesh reference and lot number		X							
Type of fixation		X							
Operative time		X							

Procedure/Assessment	Screening (Day -30 to 0)	Operative (Day 0)	Post-operative course (Day 0) Follow up	Post-operative course (Day 1) Follow up	Discharge Assessment	Post-operative course (Day 8, +/-2days) Follow Up	1 Month (Day 30, +/-1week) Follow-up	12 Months (-1/+4 weeks) Follow-up	24 Months (-1/+4 weeks) Follow-up
	Can be combined								
Mesh positioning and time		X							
Peri-operative events including adverse device effects or procedure related adverse events		X							
Surgeon satisfaction		X							
Post-operative data									
VAS pain assessment			X	X		X	X	X	X
Post-operative adverse events				X	X		X	X	X
Date of discharge					X				
Length of Hospital stay					X				
Physical exam including hernia clinical examination							X	X	X
Abdominal CT Scan								X	X
Quality of Life Questionnaire							X	X	X
Patient Satisfaction								X	X
1-month prior phone call including self-assessments								X	X
Study Exit									X
1. If Screening and Surgery occur on different days, these procedures should occur during Screening and be reconfirmed on the day of surgery. 2. No study procedures will be performed until informed consent form has been completed. Subject should be re-consented if date of original consent is greater than 30 days.									

6. Determination of Sample Size

Sample size is determined based on primary performance endpoint, assuming the superiority of ProGrip™ Self-gripping Polyester Mesh use to prevent incisional hernia vs no prevention of incisional hernia within 2-years following a midline laparotomy procedure.

The literature review showed an incisional hernia rate after midline laparotomies around 20% (9-16). Using a power ($1-\beta$) of 80% and a 5% error type I (two-sided), and considering a hypothetical incisional hernia rate of 10% for subjects with ProGrip™ Self-gripping Polyester Mesh, vs a theoretical hypothetical incisional hernia rate of 20% for subjects without any prevention following a midline laparotomy procedure, N= 108 evaluable subjects are required.

Assuming an attrition rate of 20% at 2-years, N=135 subjects will need to be enrolled.

7. Statistical Methods

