7.1.3. Analysis Sets

Statistical analysis will be performed on:

- Performance Analysis Set (PAS): includes all enrolled subjects excluding subjects who became pregnant during the follow-up, or subjects who undergo unscheduled abdominal surgery during study follow-up, which may increase the risk and cause of incisional hernia occurrence*.

*Subject follow-up data, starting from the event's occurrence, will be excluded/remove from the performance analysis.

- Per Protocol Analysis Set (PPAS): a subset of PAS excluding subjects with protocol violation and major protocol deviation(s) that may impact the primary endpoint assessment. More precisely, reason for exclusion may include but is not limited to:
 - Patient wrongly included (*i.e.* patient was enrolled but does not meet all the eligibility criteria).
 - Failure to obtain informed consent.
 - Deviation resulting from device use outside the recommended use in the IFU.
 - Patient who receives the incorrect device or device is misused
- Safety Analysis Set: includes all enrolled subjects.

Performance analyses will be run on Performance Analysis Set (PAS) and on Per Protocol Analysis Set (PPAS) as confirmatory analysis.

Safety analyses will be run on Safety Analysis set (SAS) and on Per Protocol Analysis Set (PPAS), as confirmatory analysis.

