7.9. Evaluation of Objectives

Primary Objective and Endpoint

The primary objective of this investigation is to confirm the efficacy of ProGrip™ Self-gripping Polyester Mesh to reduce the incidence of incisional hernia within 24 months post-operatively in subjects undergoing procedure with midline laparotomies.

The primary endpoint is the incisional hernia rate within 24 months of midline laparotomy assessed by CT-scan and physical examination including hernia clinical examination.

Statistical analysis of primary endpoint will be comparative. Binomial one-way test will be used to compare the observed ProGrip™ Self- gripping Polyester Mesh incisional hernia incidence rate to the 20% theoretical incidence rate (from no prevention population), using a two- sided alpha-level of 5%.

Primary endpoint will be measured using Performance Analysis Set; a confirmatory analysis of primary endpoint will be run using Per Protocol Analysis Set.

Secondary objective and endpoints

The secondary objective of this investigation is to confirm the safety of ProGrip™ Self-gripping Polyester Mesh through the occurrence of adverse device effects or procedure related adverse events following the use of ProGrip™ Self-gripping Polyester Mesh in subjects undergoing procedures with midline laparotomies.

To confirm the safety of ProGrip™ Self-gripping Polyester Mesh through the occurrence of adverse device effects or procedure related adverse events following the use of ProGrip™ Self-gripping Polyester Mesh in subjects undergoing procedures with midline laparotomies.

The following secondary endpoints will be assessed:

- Adverse event (AE) incidence reported by number, severity, seriousness and relationship to the procedure and device from the surgery to the 24-month visit: AE incidence will be measured on Safety Analysis Set.
- Time to incisional hernia occurrence: will be measured using Kaplan Meier estimates, and based on SAS, and PPAS.
- Post-operative pain at the site of surgery: will be measured on SAS and PPAS, at each postoperative timepoint: Day0 (after surgery), Day1, Day8, Day30, Month12 and Month24.
- Quality of life: will be measured on all, PAS, SAS, and PPAS, using Club Hernie QOL questionnaire, combining qualitative and quantitative data, at Month1, Month12 and Month24.
- Patient satisfaction: at 12 then 24 months, measured on PAS, PPAS and SAS
- Surgeon satisfaction, measured on PAS, SAS, and PPAS

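### The only test against 20% leaves out follow-up after unscheduled abdominal surgery or pregnancy, while the 20% carries no such condition; the same test on all implanted subjects should be pre-specified beside it

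*SAP*

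**What the plan says.** The primary objective (SAP 4.1) is to "reduce the incidence of incisional hernia within 24 months post-operatively in subjects undergoing procedure with midline laparotomies". It sets no condition on what happens to the subject after the index operation.

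The benchmark (SAP 6, protocol 15.6) is a "theoretical hypothetical incisional hernia rate of 20% for subjects without any prevention following a midline laparotomy procedure". It is attributed to a literature review, and no exclusion for later surgery or pregnancy is mentioned.

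SAP 7.1.3 defines the PAS as all enrolled subjects, less those who become pregnant during follow-up and "subjects who undergo unscheduled abdominal surgery during study follow-up, which may increase the risk and cause of incisional hernia occurrence". A footnote then says that follow-up data from the event onward are removed from the performance analysis. Protocol 15.5 and the synopsis carry the same text.

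SAP 7.9 assigns the sets: "Primary endpoint will be measured using Performance Analysis Set; a confirmatory analysis of primary endpoint will be run using Per Protocol Analysis Set". The Per Protocol set is defined as a subset of the PAS. Time to incisional hernia, a secondary endpoint, is estimated by Kaplan-Meier on the Safety Analysis Set (all enrolled subjects) and on the Per Protocol set.

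Protocol 10.2 sets the follow-up duty: "A subject must be followed for the full 24 months if the procedure was begun or completed with the study device".

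**The concern.** This is a single-arm trial with one formal test, against a fixed number. In a randomised comparison, a post-treatment exclusion might act on both arms. Here it acts on the observed rate, and nothing in the plan says that it was applied to the 20%. The reason given for the exclusion is that the events may raise hernia risk, so on the plan's own reasoning it takes higher-risk follow-up out of the mesh rate.

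Unscheduled abdominal surgery occurs after implantation and may itself follow from the index operation or the mesh. A rate in subjects who escaped it answers a narrower question than the stated objective. At stake is a claim of efficacy against 20% that might not hold in everyone who received the device. No planned analysis would show this: the confirmatory analysis shares the exclusion, and the Kaplan-Meier estimate on all enrolled subjects is descriptive.

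**Working it through.** **The plan's own figure.** From SAP 6: p0 = 0.20, p1 = 0.10, two-sided 5%, power 80%. With the normal approximation for one proportion:

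n = [1.960 × √(0.20 × 0.80) + 0.842 × √(0.10 × 0.90)]² / (0.10)² = 107.4, so 108 evaluable; 108 / 0.80 = 135 enrolled.

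Both stated figures reproduce. With the exact binomial test at n = 108, success against 20% needs 13 or fewer hernias. The lower tail is 2.1% at a true 20%, and power is 81% at 10%.

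**Assumptions not in the documents.** Let f be the share of subjects with an excluded event, taken as 5% or 10%. Let h be their 24-month hernia rate, taken as 20%, 30% or 54%. The upper value is the top of the 10-54% range in protocol 5.1. That range spans elective and emergency procedures, whereas this trial enrols elective cases only, so 54% is an outer limit.

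**Shift if the planned 10% holds only in unaffected subjects.** All-subject rate = (1 − f) × 0.10 + f × h.

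- f = 5%: 10.5% (h = 20%), 11.0% (30%), 12.2% (54%)
- f = 10%: 11.0%, 12.0%, 14.4%

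The gap between the PAS rate and the all-subject rate is therefore 0.5 to 4.4 points, against the planned 10-point effect.

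**False-success chance when the all-subject rate is truly 20%.** Two readings of SAP 7.1.3 are possible.

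*Whole subjects dropped* (the main sentence): tested rate = (0.20 − f × h)/(1 − f). The rejection limit is 12 at n = 103 (f = 5%) and 11 at n = 97 (f = 10%). With no bias, the attained lower tail is 1.8% at either size.

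*Affected subjects kept in the denominator as hernia-free*: tested rate = 0.20 − f × h, n = 108, limit 13.

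| f | h | Dropped: tested rate | Dropped: false success | Kept as hernia-free: tested rate | Kept: false success |
|---|---|---|---|---|---|
| 5% | 20% | 20.0% | 1.8% | 19.0% | 3.7% |
| 5% | 30% | 19.5% | 2.5% | 18.5% | 4.9% |
| 5% | 54% | 18.2% | about 5% | 17.3% | about 9% |
| 10% | 20% | 20.0% | 1.8% | 18.0% | 6.3% |
| 10% | 30% | 18.9% | 3.3% | 17.0% | 10.3% |
| 10% | 54% | 16.2% | 11.9% | 14.6% | 27.5% |

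With subjects dropped there is no bias at h = 20%, and the error rate goes clearly above 2.5% only when the events are fairly common or carry a high hernia rate. Below h = 20% the direction would reverse.

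**The case against.** The exclusion is pre-specified, explained, and worded alike in protocol and SAP. It can be defended as a choice of target: how well the mesh protects the index suture line, leaving aside hernias produced by a second operation. An all-enrolled analysis would count such hernias against the mesh. This stands as a reason to keep the PAS estimate, and it is why the documents do not support a stronger demand that the primary set be replaced or that both tests must reject. It does not explain why that narrower rate alone is compared with an unrestricted 20%.

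A reader might infer that the PAS rate *is* biased low. The documents do not establish that. They say only that the events may raise the risk, and whether the studies behind the 20% set aside reoperated or pregnant patients cannot be seen here. The direction could also reverse under a mixed rule that keeps hernias recorded before the event but drops affected subjects without one. With 10% affected at twice the risk, this happens once more than about 20% of affected subjects had an earlier recorded hernia. The plan does not state that rule either.

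A reader might also take the 3.7% to 27.5% figures as the likely error rates. They require a removed outcome to be scored as no hernia. The plan nowhere says this, and it fits poorly with analysis of available data without imputation (protocol 15.1, SAP 7.4).

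Finally, hernia outcomes in all enrolled subjects are not ignored, since the Kaplan-Meier analysis covers them. That narrows the gap to one missing test. Pregnancy probably adds little, because women planning it are excluded at entry (protocol 10.4).

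**Conclusion.** The point holds as a mismatch between what is tested and what it is tested against. The PAS conditions on the absence of later abdominal surgery or pregnancy, the stated benchmark does not, and no planned test against 20% covers all implanted subjects. On the plan's premise that these events raise hernia risk, the tested rate is expected to be low relative to 20%.

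The size cannot be determined from the documents. Under the assumed 5-10% affected and 20-54% hernia rate among them, with a true all-subject rate of 20%, false success runs from about 1.8% (no inflation) to 11.9% if whole subjects are dropped. The larger range applies only under the unstated hernia-free scoring. The calculation of 108 and 135 is correct and is not in question.

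**What to change.** In SAP 7.1.3 and 7.9, and in protocol 15.5:

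1. Pre-specify the same binomial test against 20%, run as an exact test, on all enrolled (implanted) subjects. Count every incisional hernia found within 24 months, whatever later abdominal surgery or pregnancy occurred.
2. Report it beside the PAS result, and label the PAS result as the hernia rate in the absence of later abdominal surgery or pregnancy.
3. State that the efficacy conclusion will be qualified if the two tests disagree.

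The cost is SAP and protocol wording plus one more run of the same test. No new visits or procedures are needed, since protocol 10.2 already asks for full follow-up.

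There are three downsides. The all-enrolled rate may be less favourable and will include some hernias caused by a second operation. Subjects whose mesh is removed leave the study 30 days later (protocol 11.7.8 and 11.13.6), so their 24-month outcome will be missing and should be reported as such. Power for the added test stays at 81% with 108 evaluable subjects if 10% is the all-subject mesh rate; it falls to about 76% if that rate is 10.5% and to about 70% if it is 11.0%.

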7.2. General Methodology

At the exception of Primary endpoint analysis which will be comparative (see details in section 7.9 Evaluation of Objectives), statistical analysis will be mainly descriptive.

Some subgroup comparative analyses may be run in addition to primary and secondary endpoints, to assess impact of demographic characteristics, risk-factors, indication for surgery, operative data and surgical technique applied.

- Qualitative variables will be described by their absolute and relative (%) frequencies of each class or value, and by two-tailed 95% confidence intervals.

- Quantitative variables will be described by their mean, standard deviation (SD), extreme values (minimum and maximum values), and number of missing data and by two-tailed 95% confidence intervals.

Continuous variables will be summarized using counts, means, and standard deviations, medians, minimum, maximum and 95% confidence Interval (CI).

Categorical variables will be summarized using absolute and relative (%) frequencies of each class or value, and by two-tailed 95% confidence intervals.

Statistical analysis will be implemented on overall subjects, using 1 analysis sets, as described previously (Section 7.1.3).

Comparative subgroup analyses will be performed using:

- Pearson Chi-square test or Exact test will be used (as appropriate) for categorical data
- Student t-test or Wilcoxon rank sum test will be used if assumptions or t-test are not verified for continuous data.

Primary and secondary endpoints analyses are described in detail in section 7.9 *Evaluation of objectives*.

Statistical analyses will be run using SAS® v9.4 system, and statistical outputs will be provided in text files.

7.3. Center Pooling

The study will be conducted in a minimum of 6 and maximum of 10 investigational sites. Baseline and surgical data will be summarized for overall subjects and for each site separately, to confirm homogeneity of subject's characteristics between sites.

Enrollment will not exceed 25 subjects per site, which avoid imbalance between sites.

Primary and secondary endpoint analysis will be run on overall subjects and sites.

7.4. Handling of Missing, Unused, and Spurious Data and Dropouts

No data imputation will be performed for missing data unless otherwise noted in statistical analysis plan. All practical monitoring and follow-up steps will be taken to ensure complete and accurate data collection.

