## **11.13 Subject Exit, Withdrawal or Discontinuation**

### **11.13.1 Study Exit**

A study exit CRF is required for all subjects. Prior to exiting a subject from the study, it is recommended to follow the subject until all ongoing system and/or procedure related AEs are resolved or unresolved with no further actions planned. Following exit, subjects will continue to receive standard medical care. Upon exiting from the study, no further study data will be collected or study visits will occur for the subject. All data available through the time of the subject's exit will be used for analysis.

Subjects are urged to remain in the study as long as possible but may be exited from the study for any of the following situations:

- Study completed
- Subject lost to follow-up
- Subject death
- Subject chooses to withdraw (e.g., consent withdrawal)
- Investigator deems withdrawal necessary (e.g., medically justified, inclusion/exclusion criteria not met, failure of subject to maintain adequate study compliance)
- Mesh removal

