# 15. Statistical Design and Methods

## 15.1 General Aspects of Analysis

For each of the objectives the available data will be summarized and missing data will be discussed. The main analysis of the study objectives will be based on available data and missing data will not be imputed unless otherwise noted in the statistical analysis plan. All practical monitoring and follow-up steps will be taken to ensure complete and accurate data collection. Deviations to the statistical analysis plan (SAP) will be reported per section 11.12 (Deviation Handling).

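### The SAP does not say whether a hernia-free subject who leaves before month 24 counts in the primary denominator, and it plans no sensitivity analysis for missing outcomes

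*SAP*

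**What the plan says.** - **Test and set.** SAP 7.9 compares the observed hernia rate within 24 months with 20% by a binomial test at two-sided 5%. "Primary endpoint will be measured using Performance Analysis Set", and "a confirmatory analysis of primary endpoint will be run using Per Protocol Analysis Set".
- **PAS.** SAP 7.1.3: the set "includes all enrolled subjects excluding subjects who became pregnant during the follow-up", or who have unscheduled abdominal surgery. A month-24 assessment is not required. The footnote reads differently from the main text: "Subject follow-up data, starting from the event's occurrence, will be excluded/remove from the performance analysis".
- **Missing data.** SAP 7.4: "No data imputation will be performed for missing data unless otherwise noted in statistical analysis plan". Protocol 15.1: "The main analysis of the study objectives will be based on available data and missing data will not be imputed", unless the SAP notes otherwise. It adds that missing data will be discussed. No SAP section notes an exception.
- **Early exit.** Protocol 11.13.1: "All data available through the time of the subject's exit will be used for analysis".
- **Sample size.** SAP 6 and Protocol 15.6 need 108 evaluable subjects and enrol 135 for 20% attrition. *Evaluable* is not defined.
- **Time to hernia.** SAP 7.9 plans Kaplan-Meier as a secondary analysis on the Safety Analysis Set and Per Protocol Analysis Set (PPAS). It is not listed for the PAS and not compared with 20%.

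**The concern.** A binomial rate needs every subject classified as event, non-event or excluded. A hernia seen before exit is an event within 24 months and is kept under Protocol 11.13.1. A subject who leaves hernia-free has no 24-month outcome, and two rules are open:

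- **Whole PAS:** the subject stays in the denominator, in effect as hernia-free at 24 months.
- **Observed status:** the subject is left out, while leavers with a hernia stay in.

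A no-imputation clause does not choose between them. The PAS definition can be read for the first; the available-data principle and the 108 evaluable of 135 lean to the second. With 27 leavers planned, the choice can decide the verdict. The study is single-arm and unblinded, so a denominator left open could be fixed after the counts are known. Exit may also be linked to outcome: under Protocol 11.13.6 a subject exits 30 days after mesh removal.

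**Working it through.** **Inputs from SAP 6 and 7.9:** null rate 20%, expected rate 10%, two-sided 5%, power 80%, 108 evaluable, 135 enrolled, attrition 20%.

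**1. The plan's own figure.** n = [(1.960·√(0.2·0.8) + 0.842·√(0.1·0.9)) / 0.10]² = 107.43, so 108; 108/0.80 = 135. Both reproduce. Exact power at 108 is 0.81. The sample size is not in error.

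**2. Success limits.** Largest x with P(X ≤ x | n, 0.20) ≤ 0.025: 13 at n = 108 to 112, and 17 at n = 135.

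**3. Example.** Suppose 108 completers have 12 hernias, 2 of 27 leavers had a hernia at month 12, and 25 leave hernia-free. There are 14 hernias in all (p = twice the lower tail).
- Observed status: 14/110 = 12.7%, p = 0.064, failure.
- Whole PAS: 14/135 = 10.4%, p = 0.004, success.
- Kaplan-Meier, assuming 6 of the 12 completers' hernias were seen at month 12 and all exits came after that visit: 1 − (127/135)(96/102) = 11.5%, 95% CI 6.9% to 18.7%.

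**4. Whole PAS at a true 20%.** Let a be attrition and s the share of leavers' hernias seen before exit (assumed). The observed rate is q = 0.20·[(1 − a) + a·s], and false success is P(X ≤ 17 | 135, q).

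| s | q at a = 20% | False success |
|---|---|---|
| 0 | 0.160 | 16.8% |
| 25% | 0.170 | 10.3% |
| 50% | 0.180 | 5.9% |
| 75% | 0.190 | 3.2% |

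A two-sided 5% test allows 2.5% in this direction. At 10% attrition the largest value is 5.9%.

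**5. Observed status.** The expected rate is about p·[(1 − a) + a·s] / [(1 − a) + a·s·p]. For p = 0.20, a = 0.20 and s = 0.5 this is 0.18/0.82 = 22.0%; for s = 0.75 it is 0.19/0.83 = 22.9%; for s = 0 it is 20.0%. The rate is overstated because leavers with a hernia count and leavers without one do not.

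**6. Simulation.** N = 135, detection at months 12 and 24, dropout unrelated to hernia. Assumed, not in the documents: 50%, 62.5% or 75% of hernias detectable by month 12; exits all before that visit, all after it, or half and half. Kaplan-Meier success means an upper log-log 95% limit below 20%.

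| | 20% attrition | 10% attrition |
|---|---|---|
| Observed status, power at 10% | 0.60 to 0.79 | about 0.77 to 0.85 |
| Observed status, false success at 20% | at most about 2% | at most about 2% |
| Opposite verdicts of the two rules, true 10% | about 19% to 31% | about 9% to 12% |
| Kaplan-Meier on PAS, mean at a true 20% | 20.0% | 20.0% |

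At 20% attrition, Kaplan-Meier has false success of 1.5% to 1.9% and power of 0.77 to 0.85.

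**7. Tipping point.** With 11, 12 or 13 hernias in 108 completers and 27 unknown, success against 17/135 is lost if 7, 6 or 5 of the 27 had a hernia. The chance of that many is 0.29, 0.46 or 0.65 if leavers' risk is 20%, and 0.015, 0.047 or 0.127 if it is 10%.

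**The case against.** The best defence is that the documents lean to observed status: available data, no imputation, and 108 evaluable of 135. That rule errs on the cautious side, with false success at most about 2%. Late visits are analysed (Protocol 11.3), missed visits are chased (11.13.5), discontinuation reasons are tabulated (SAP 7.1.1), missing data will be discussed, and Kaplan-Meier on the Safety Analysis Set already covers every PAS subject.

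Much of this stands. Whole-PAS division is the less supported rule, and its 16.8% is the extreme case in which none of the leavers' hernias is seen. But a lean is not a rule, and the favoured rule falls short of the stated power at planned attrition. None of the safeguards assigns an outcome or shows how far the result depends on missing ones. The PPAS rerun is defined by deviations, and the planned Kaplan-Meier analysis is not tied to the primary rate or to 20%.

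A reader might also infer a third rule: drop everyone without a month-24 assessment, which gives 12/108, p = 0.021, in the example. The documents do not support it. Protocol 11.13.1 keeps data through exit, and the endpoint is hernia within 24 months, so a hernia seen at month 12 cannot be discarded. Error rates for a completers-only analysis are therefore not evidence here.

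**Conclusion.** The concern holds in this form: the treatment of hernia-free leavers in the primary denominator is not stated, and no analysis tests sensitivity to missing outcomes. At 20% attrition, whole-PAS division exceeds the 2.5% tail in every case shown and 5% in three of four. Observed status keeps error low but gives power of 0.60 to 0.79 instead of 80%. At 10% attrition both problems shrink: false success is at most about 6%, and power is about 0.77 to 0.85.

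These sizes rest on assumed detection timing, exit timing, attrition and leaver risk. The gap in the text does not depend on them. Two stronger readings are not supported: that the sample size is wrong (it reproduces), and that the plan ignores missing data (it states an available-data principle). It should be fixed before the final analysis.

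**What to change.** 1. In SAP 7.4 and 7.9, state that a hernia-free subject without a month-24 assessment is not counted as hernia-free at 24 months and that a hernia seen before exit is kept. Define *evaluable*.
2. Add the 24-month Kaplan-Meier cumulative hernia incidence on the PAS with a two-sided 95% CI shown against 20%. Time it by nominal visit, because the month-24 window runs to 25 months (Protocol Table 3). Add a cumulative-incidence version with death as a competing event: death is a listed exit and recent cancer a listed risk factor.
3. Say which analysis decides. SAP 7.5 commits to a single primary test. Either the binomial test remains that test and Kaplan-Meier is supportive, or the reverse is pre-specified. This matters: in the scenario with half of hernias detectable by month 12 and all exits afterwards, power is 0.67 for the binomial test and 0.83 for Kaplan-Meier, so they disagree in at least 0.83 − 0.67 = 16% of trials at a true 10%.
4. Add a tipping-point analysis over subjects with missing month-24 status, reported at leaver risks of both 20% and 10%. Kaplan-Meier assumes that hernia-free leavers carry the same later risk, so it does not replace this.
5. List the PAS for time to hernia. Reconcile SAP 7.1.3, whose main text excludes pregnant or re-operated subjects while its footnote removes only later data, before stating how they are censored.

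**Cost:** a SAP amendment and a few outputs from data already collected. The reported rate may be less favourable than events over all enrolled. If the observed-status binomial test decides, it is conservative, and its expected power at 20% attrition should be restated.
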